In order to reflect user needs into the design, we will use an iterative approach with rounds of interview sessions with 10 dyads of children and parents per cycle for up to 3 cycles (**Fig 2**). Each interview session will be a one-hour semi-structured interview. During this interview the trained RA will solicit overall impressions about the design of the interface, perceived strengths and weaknesses of the approach as well as any suggestions for improving the content or functionality of the system. Following each cycle, changes will be made to the user interface based on problems and preferences identified during the previous cycle. The revised user interface will then be evaluated in a subsequent cycle (for a total of up to 3 cycles). The same participants will be recruited for each cycle.

Once the design has been finalized and the iterative design process has led to the finalized overall design approach, we will organize think-aloud sessions with 5 children-parent dyads (new participants; not previously involved in the iterative design process) to identify any potential usability issues (during months 8 and 9) and identify opportunities for improvement at a more granular level. We will use a mobile usability laboratory, including an electronic tablet loaded with the web application, data for 2 simulated dyads for testing, Morae recorder software (version 3.3). Co-I ([name]) and RA will directly observe (and audio-record) 10 users individually (5 children and 5 parents) as they interact with the system. In addition, each user will be asked to "think aloud" about how they make specific choices in their interactions, talk through their engagement with the tools, verbally describe their actions and strategies when interacting with the tools, any suggestions, what they like or dislike, and whether or not navigation is intuitive.^{51,52} As Nielsen points out,⁵³ running more test subjects increases the number of problems found but with progressively diminishing returns; since five test subjects will lead to identifying 77-85% of usability problems, it is recommended to engage 5 test users for think aloud sessions (in our case as we recruit dyads, we will have 5 children and 5 parents in the think-aloud sessions). A think-aloud protocol is based on the concept of participants being asked to think aloud as they interact with the

system and perform a set of specified tasks. Participants are asked to say whatever comes into their mind as they complete the task.⁵⁴ This might include what they are looking at, thinking, doing, and feeling. We will identify a series of tasks (such as setting goals, accessing graphs and educational resources) and ask participants to verbalize their thoughts as they try to complete these tasks. This provides insight into the participant's cognitive processes (rather than only their final impression), making thought processes as explicit as possible during task performance.⁵⁵ All verbalizations during these sessions will be transcribed and then analyzed.

Data Analysis. Quantitative data from the *Usability Error and Efficiency Documentation Form* will be analyzed using SAS 9.3. using descriptive statistics. Descriptive statistics will be calculated for quantitative usability measures (i.e., response time and accuracy) for specific tasks. Incomplete tasks or tasks that take longer than planned, will indicate a need for design improvements based on user feedback. Audio-recordings will be transcribed and then analyzed by members of the research team. Following procedures explicated by Braun and Clarke,⁵⁶ researchers will employ thematic analysis techniques to identify, analyze, and report patterns in the data. First, they will review all transcribed data, creating memos describing their initial impressions and noting areas for additional exploration. Then, they will meet to generate an initial list of codes. Over a series of face-to-face meetings, they will use NVivo 11 qualitative data management software to code the data with existing, refined, or newly created codes. Approximately halfway through qualitative data collection, researchers will begin sorting coded data into broader themes. Finally, researchers will define and name each theme, highlighting relationships among themes. Disagreements about themes will be handled through analyst consensus. Identified glitches, feedback, recommendations will be synthesized for programmers.

Aim 2. Determine feasibility and initial efficacy of the SMID with children with JIA in a pilot RCT. We will determine study accrual and dropout rates as well as levels of patient acceptability and engagement in a pilot randomized controlled trial (RCT) comparing usual care to SMID intervention. Preliminary effect sizes of the SMID will be determined in youth receiving treatment compared to usual care on primary outcomes of actigraphy sleep duration, sleep quality, and feasibility/acceptability, and secondary outcomes of child and parent self-management (activation, motivation, self-efficacy), technology use, recommendations for innovative sleep monitoring. We hypothesize that children who receive technology-based SMID vs. those who receive Usual Care will achieve increased sleep duration and efficiency (quality), immediately post-treatment and at 3 month follow-up.

Sample. Sixty children, 9-11 years, diagnosed with JIA and one parent will be recruited from the Pediatric Rheumatology Clinic at SCH and remotely via a flyer on the JIA foundation website.

Recruitment. At SCH, the clinical research assistant (CRA) will give eligible JIA families a study information flyer; the flyer will also be posted on the WA JIA website. For both SCH and the JIA website, interested families will contact the CRA by calling a phone number on the study flyer. The CRA will describe the study and screen for participation. Interested participants will be sent a consent/assent forms by mail, with a prepaid envelope. The recruitment methods were fruitful in our prior studies. Inclusion and exclusion criteria for JIA children and parents is above. Gender/minority inclusion: Girls and boys are eligible; we expect to enroll more Caucasian girls because the heightened disease prevalence among Caucasian girls and its relatively low prevalence in other ethnic groups.^{57,58} JIA patients seen at SCH approximate the national ratio of female:male patients 4:1 and 95% Caucasian. Biologic variables: We will include sex as covariate in the statistical analysis due to the potential confounding effect on sleep.

Measures. **Table 2** shows the measurement plan for the study assessments.^{2-27,59-72}

Power. We will enroll 60 dyads for a projected sample size of 50 (25/group), assuming 15% attrition. This meets recommendations for pilot trials⁷³ and provides 80-90% power to detect moderate effects based on a RM ANOVA model with three repeated measures and a correlation of 0.3 between the measurements. This power calculation was based on the moderate to large effect sizes for our outcomes of interest (total sleep time, $d=.48$; health related quality of life, $d=.51$; and fatigue, $d = .79$) found in our previous research.

Intervention. All JIA children and parents will receive access to the SMID program, which consists of two separate, password-protected web programs, one for child access and one for parent access. The intervention is completed in an 8-week period. The program design and treatment content of SMID follow cognitive behavioral, social learning, and family systems frameworks. Given the important role of parents in children's self-management of sleep deficiency, parents are engaged throughout the intervention period in their own treatment content intended to support their child's goals and to learn strategies to modify their own behavior in response to their child's sleep deficiency. The child modules will include: sleep education, sleep skills training

(e.g., daily record of activities before bed, sleep routine and schedule), lifestyle changes, relaxation techniques positive coping, relapse prevention, reward systems for activity participation. The parent modules include: sleep education, use of attention and praise to increase positive coping, strategies to support self-management skills and goals, modeling and communication. The program is designed to enhance self-management of sleep. Children set structured and personalized goals aimed at improving their self-management skills and sleep. Given the importance of

Table 2: Measures

Concept	Measure: Target and Description including Duration and Frequency of Administration
Sleep Deficiency	
Inadequate Sleep	Actigraphy continuous recording of child's sleep-wake activity using (Actiwatch-L, MiniMitter-Respironics, Bend, OR). ²⁵⁻²⁷ Derived parameters: total sleep time, sleep efficiency, sleep onset (bedtime), sleep offset (wake time), wake after sleep onset; (T1,T2,T3) Sleep Diary daily recording of child's pre-bedtime activities (media use, sports, caffeine intake), daily sleep (time to bed, sleep onset, # night awakenings); medications, & daytime activities (T1,T2,T3)
Sleep quality	Actigraphy & Sleep Diary-see above; (T1,T2,T3) Child Sleep Wake Scale (CSWS) ⁵⁹ 40-item parent report of sleep initiation during past month. Domains: going to bed, falling asleep, awakening, reinitiating sleep & wakefulness; yields total score; $\alpha=.89$ (T1,T2,T3)
Sleep hygiene	Children's Sleep Hygiene Scale (CSHS) ^{60,61} 17 item parent report of activities around sleep during past month; sleep hygiene domains: pre-bedtime activities, bedtime routine, stable bedtime; yields total score; $\alpha=.78$; (T1,T2,T3)
Self-Management	
NINR CDEs Self-efficacy	Self-Efficacy ^{62,63} 9-item parent and child report of their confidence in carrying out sleep-related behaviors (T1,T2,T3)
Motivation	Index of Self-Regulation (IRS) ^{64,65} 12-item parent and child report of motivation; subscales (recondition, stimulus control, behavioral monitoring); Established construct validity; IC reliability .72-.87 across different demographic groups and chronic illness conditions. (T1,T2,T3)
Activation	Patient Activation Measure ⁶⁶ 13-item parent and child report of knowledge, skill, & confidence for self-management; Adequate construct validity; IC reliability .81-.96; $\alpha=.91$; demonstrated across age groups and different populations (T1,T2,T3)
Daytime Function & Health Outcomes	
Fatigue	Multidimensional Fatigue Scale ⁶⁷ 18-item child and parent-report of fatigue in last month; yields 3 subscale (general fatigue, sleep/rest fatigue, cognitive fatigue) & total fatigue score. Reliability total $\alpha=.95$, subscale .90-.93 (T1,T2,T3)
HRQoL Emotional Health	PedsQL Generic Core Inventory ^{68,69} 23-item child and parent-proxy report of physical, social, emotional, school function; yields total score & 2 subscale scores (Physical & Psychosocial Health). Reliability total $\alpha > .88$, subscales .80-.84. (T1,T2,T3) PROMIS anxiety ^{70,71} 8-item child report of anxiety including fear, worry, hyperarousal (tension, nervousness) in the past week; Reliability .88 (T1,T2,T3)
Descriptives	
NINR Demographics	Parent report of demographics (parental age, education, race/ethnicity, child age, sex, race/ethnicity), medical and family history; Number of months since JIA diagnosis (T1)
Pain	Numeric Rating Scale (NRS) ⁷² child report of pain intensity with an 11-point NRS (0=no pain, 11=worse pain) (T1,T2,T3)-will be included in daily diary

homework and practice to change behavior, several components (e.g., positive feedback loops) actively encourage user attention and motivation in order to promote skills acquisition and rehearsal. The intervention will be interactive and personalized with tailored feedback. Using a diary function on the web site, children track their sleep in real-time and can generate customized reports and graphs from their data. Modules will take an estimated 20 minutes to complete and will include multimedia elements to enhance learning. Participants will be asked to spend additional time practicing skills and completing assignments at the end of each module. A message center will allow each child and/or parent to ask questions as they progress in the program. The PI will review messages, provide individualized feedback through Web message center. The web site uses a multimedia-rich format (e.g., animations, videos, audio clips) to deliver content. The website is built on a responsive platform and can be viewed on multiple devices (e.g., smartphones, laptops, tablets) to increase ease and flexibility of use. All app and website content is (a) written at a grade 4th grade reading level, (b) developmentally appropriate for 9-11 year-olds, and (c) is based on a unifying theme/narrative.

Measurement Plan. Assessment will occur at (T1 baseline), immediately after intervention (T2) and repeated at 3 months post-intervention (T3) for both the SMID and usual care groups. All questionnaires will be administered using REDCap, a secure web-based tracking and on-line data acquisition system. Children will wear an actigraph a reliable and validated measure of sleep²⁵⁻²⁷ on their non-dominant wrist for 10 consecutive days, and complete an electronic symptom diary. After 10 days, parents will mail back the actiwatches in a prepaid self-addressed envelope used in PIs prior sleep studies.^{1,27,35} Actigraphy data will be downloaded, scored, and a member of the team will follow up with parents to discuss the baseline sleep patterns within 1 week. Estimated time burden is 20 minutes for children and 10 minutes for parents. Response burden is minimized by online administration, which saves and stores responses.

Perceived usefulness and acceptance. About one third of all participants (33%; 20 out of 60 dyads) will be interviewed at study exit to assess their overall perceptions of the web-based program, the perceived usefulness and ease of use. All interviews will be conducted by trained RA in person or via telephone and will

be digitally audio-recorded. Specifically, questions will address the perceived impact of the system on sleep self-management, barriers and facilitators to use and whether children and parents would foresee future use and recommend the system to others. Audio-recordings will be transcribed and then analyzed by members of the research team. Following procedures explicated by Braun and Clarke,⁵⁶ described above.

Randomization. Following completion of baseline assessments, participants will be randomized to one of two treatment arms. Across groups, children will continue to receive their usual specialty medical care for JIA. A blocked randomization scheme will be generated using an online program to derive randomization assignment, programmed in the Internet sleep intervention, and not accessible to study investigators. Enrolled participants will be continuously randomized.

Usual Care. This treatment arm will receive usual JIA care, including annual Rheumatology clinic visits, medications, routine clinical and laboratory tests, physical therapy, follow-up appointments. Sleep intervention is not a part of usual care. The CRA will routinely review medical records and document any changes in medical care received during the intervention period.

Data Analysis Plan. Descriptive summaries of recruitment outcomes (number of contacts made related to interest in the study, numbers screened, eligible, enrolled, completed), and retention (number of parents and children who completed the study, dropouts, reasons given, timing of withdrawals) will be reported. **Treatment engagement** will be measured by completion of at least one module in the SMID program while **adherence** is defined as the completion of 5 or more modules. The administrative interface of the SMID program will have a tracking system in place for recording each time a user logs onto the web program. **Overall usage statistics** will include monitoring of program usage (number of logins, duration of time spent completing, time spent on a page or feature). Each module will contain multiple-choice quizzes concerning the content presented as well as behavioral assignments, fill-in-the-blank fields, and use of the diary tracker. All data fields that are completed within modules are stored, generating a comprehensive activity record of module specific use including self-management tasks. Exit interviews will be assessed as described above.

Data will be reviewed for completeness and errors including consistency checks for relevant variables. Tabular and graphical methods of data exploration including frequency tables and scatterplots will be used to explore distributions of study variables. We will adjust for sex, and considered use of either RM ANCOVA or generalized estimating equations (GEE) to evaluate intervention effects. We prefer GEE since it allows us to account for clustering of repeated assessments within individuals as well as the longitudinal nature of the data and provides higher power. Missing data will be examined for patterns and we will employ GEE multiple imputation to carry out ITT analysis. Single degree of freedom contrasts by group will be examined if there are significant changes in sleep measures from pre- to post-treatment and/or from pre- to 3-month follow-up for SMID vs Usual Care. Secondary treatment outcomes will be examined using GEE to explore for mean changes across time and between groups using interaction terms and contrasts. The range of outcome measures will allow us to obtain experience with alternative measures of sleep, self-management measures that will inform our future research. Outcome data will also be used to generate effect size point estimates for the future large-scale trial. **Design Considerations, Alternative Strategies and Timeline.** Project constraints on research time and resources will pose study limitations, which we have adjusted for in the study design and timeline. As the study requires participant enrollment for 5 months, we anticipate some challenges around retention, and have addressed this with a number of strategies described below. Co-I, [name] successfully recruited and retained youth with chronic pain in Web-based interventions over a period of 12 months (>90% retention). An attention control group and other parent/child variables were considered but feasibility, acceptability, and proof of concept were prioritized for this initial phase. **Rigor and Transparency** will be ensured by: 1) the proposed methods (usability, expert panel, parent/child input); 2) use of successful retention strategies from prior studies; 3) documentation of attrition; 4) sample size derived from a priori power analysis; 5) statistical methods to account missing data and change overtime. **Retention.** We will make every effort to retain participants with fruitful methods used in our prior studies including: 1) automated reminders built into the Web program; 2) phone calls scheduled at convenient times, 3) incentives for completion of each assessment (\$20 gift card/each Aim 1; Aim 2 [T1 \$40 gift card each; T2 \$60 gift card each; T3 \$80 gift card each]), 3) semi-structured interviews *prior to* intervention development; and 4) exit interviews post-intervention. **Strengths** include: 1) successful recruitment of JIA children; 2) expertise in sleep, technology-based interventions, usability assessments; 3) leveraging of successful methods in a prior Web-based interface; 4) development of the first low resource demand, convenient, and personalized sleep self-management intervention for JIA. Findings generated will address important methodological issues needed to develop innovative sleep self-management intervention for children with chronic illnesses and their parents.

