population. Based on the success of self-management programs in other chronic illness populations, we expect that similar approaches to implementing a sleep self-management intervention in JIA will also be feasible and effective.

INNOVATION. Parents and children routinely use technology as a source of health information. Most children and parents do not have access to sleep self-management interventions in their communities. Access to Web-based technologies among youth is high^{30,31} making the proposed intervention have extended reach and potential impact. The intervention itself is innovative in several ways, including the focus on the parent-child dyad, which offers an important opportunity to explore co-participation, and its emphasis on building self-management skills to effect changes in sleep health. The school-age years are an important age for healthy sleep habits and learning self-management skills³²⁻³⁴ under parental supervision that contribute to improved health outcomes. This proposal builds on our prior collaborations with the *Center for Innovation in Sleep Self-Management* (Drs. [name] [Co-Director], [name] [Core Director], [name] [Advisory board]).

PRELIMINARY DATA. The team has extensive experience in JIA, sleep, use of actigraphy, development and testing of Web-based interventions, usability science, and intervention research in children and families.

Sleep Deficiency in JIA. Our prior work shows that 40% of JIA children have sleep deficiency as measured by actigraphy, with an average duration of 7.5 hours and poor sleep quality (< 85%).^{1,2} Sleep deficiency was associated with fatigue and increased anxiety.³⁵ None of the children had been previously screened or assessed for sleep deficiency.

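### The 80-90% power statement names no tested effect, alpha or scale of d, and is not shown for the between-group sleep hypothesis: if d=0.48 is a between-arm difference, the planned pre-to-post contrast has about 29-38% power

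*Combined protocol and SAP*

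**What the plan says.** The Power paragraph under Aim 2 of the Research Strategy plans 60 dyads, projects 50 analysable (25 per group) after 15% attrition, and says this "provides 80-90% power to detect moderate effects based on a RM ANOVA model with three repeated measures and a correlation of 0.3" between measurements. It adds: "This power calculation was based on the moderate to large effect sizes for our outcomes of interest", listing d=0.48 for total sleep time, 0.51 for health-related quality of life and 0.79 for fatigue, all from previous research. The sample size has a second justification: "This meets recommendations for pilot trials".

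The Aim 2 hypothesis compares the arms: "We hypothesize that children who receive technology-based SMID vs. those who receive Usual Care will achieve increased sleep duration and efficiency (quality"), immediately after treatment and at follow-up. The Data Analysis Plan weighs RM ANCOVA against GEE and says "We prefer GEE since it allows us to account for clustering of repeated assessments within individuals". It then plans the arm comparison: "Single degree of freedom contrasts by group will be examined if there are significant changes in sleep measures from pre- to post-treatment" or from baseline to the 3-month follow-up, SMID against usual care. The Rigor and Transparency list includes "sample size derived from a priori power analysis".

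**The concern.** An RM ANOVA with two arms and three visits has three testable effects: time, group, and group by time. The Power paragraph does not say which one the 80-90% belongs to. It gives no alpha, and none appears elsewhere. Nor does it say whether d is between arms or within children, or which SD it is scaled by. These choices decide whether the figure describes the trial's hypothesis.

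Actigraphy sleep duration is a named primary outcome with a directional between-group hypothesis. A reader will take 80-90% as a 10-20% chance of missing the assumed sleep effect. If d=0.48 is a between-arm difference in single-visit SDs, the planned contrast misses it about 71% of the time (100 − 29), and a non-significant sleep result would carry far less information than the stated power suggests.

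**Working it through.** **Inputs.** From the Power paragraph: n=25 per arm (N=50), m=3 visits, correlation ρ=0.3, d=0.48, 0.51 and 0.79. Assumed because the documents do not say: two-sided alpha 0.05, equal variances and equal correlations across visits, complete data on the 50.

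**Reproducing 80-90%.** For within-subject effects, use the noncentral F with λ = f²·N·m/(1−ρ) = f²·150/0.7 and df 2 and 96.

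- *Time effect, both arms pooled, change d at T2 and T3.* f = d√2/3. For d=0.48, f=0.226, λ=10.97, power 84.0%. For d=0.51, f=0.240, λ=12.39, power 88.3%. With a linear change (0, d/2, d), power is 71.6% and 77.1%.
- *Group by time with f = d/2.* f=0.24 gives λ=12.34 and power 88.2%. The conventional moderate f=0.25 gives λ=13.39 and 90.8%.
- *Group main effect with f=0.24.* λ = f²·150/(1+2ρ) = f²·150/1.6 on 1 and 48 df gives 62%, which does not reproduce the range.

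**What the two reproducing routes mean.**

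- The time test is blind to the arms. In simulation (40,000 trials), when both arms change by 0.48 it rejects 83.8% of the time, while the group-by-time test rejects 5.0%, which is alpha.
- For arm differences of (0, d, d), the group-by-time f is d/√18. So f=0.24 means d = 0.24×4.243 = 1.02 SD, and f=0.25 means 1.06 SD. Putting d=0.48 in correctly gives f=0.113, λ=2.74 and power 28.9%.

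**Power for a between-arm d.** Use the noncentral t with SE = √(k·2/25) in single-visit SDs:

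- Pre-to-post change contrast: k = 2(1−ρ) = 1.40, SE 0.335, df 48.
- Baseline-adjusted, one visit: k = 1−ρ² = 0.91, SE 0.270, df 47.
- Baseline-adjusted T2/T3 mean: k = (1+ρ)/2 − ρ² = 0.56, SE 0.212, df 47.

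If d is in change-score SDs, multiply it by √1.4 first (0.48 becomes 0.568). For d=0.48 in the change contrast, the noncentrality is 0.48/0.335 = 1.43 (single-visit) or 0.568/0.335 = 1.70 (change-score).

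| d | Scale of d | Pre-to-post contrast | Adjusted, one visit | Adjusted T2/T3 mean |
|---|---|---|---|---|
| 0.48 | single-visit SD | 29% | 41% | 60% |
| 0.48 | change SD | 38% | 54% | 75% |
| 0.51 | single-visit SD | 32% | 46% | 66% |
| 0.51 | change SD | 42% | 59% | 80% |
| 0.79 | single-visit SD | 64% | 82% | 95% |
| 0.79 | change SD | 78% | 92% | 99% |

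Simulation agrees for d=0.48 on the single-visit scale (29.1%, 40.8%, 59.6%). The preferred GEE with robust standard errors gives 32.1% for the contrast, but its type I error is then 6.1%.

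**Sensitivity at d=0.48.** A higher correlation raises power for the contrast on the single-visit scale to 38% (ρ=0.5) or 57% (ρ=0.7). At ρ=0.3, one-sided 0.05 with all 60 observed gives 46% (single-visit) or 58% (change SD).

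**Detectable difference.** The contrast has 80% power for 0.96 single-visit SD. Its 95% CI half-width is about 2.011×0.335 = 0.67 SD.

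**The case against.** The strongest reply is that the figure does reproduce, so no arithmetic error is shown, and that one reproducing route, the standard group-by-time calculation at a moderate f, does compare the arms. This stands. A reader might infer that the sponsor powered the wrong test. The documents do not support that: they name no test, the group-by-time reading fits the wording at least as well, and the time route needs the full change to be present at both follow-ups. What remains is that the group-by-time route reaches 80-90% only for arms about 1 SD apart, which is not the cited 0.48.

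Second, the 29% is the lowest of several conditional values. Also true. A reader might take it as the trial's power, but the scale of d is unknown. The Preliminary Data section does not settle it. It reports prevalence ("Our prior work shows that 40% of JIA children have sleep deficiency as measured by actigraphy") and associations, and the one RCT it describes reports pain-related outcomes; a summary's silence does not say what d is. Some combinations do reach 80% at d=0.48. For example, d in change-score SDs with a baseline-adjusted T2/T3 mean gives 82% with all 60 observed (two-sided) or 84% with 50 (one-sided). The plan states none of these assumptions.

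Third, this is a pilot. N also rests on pilot recommendations, the aims include effect-size estimation, and no go/no-go rule depends on significance. This limits the weight of the point. A reader might infer that 60 dyads are too few for the trial's purpose; the documents do not support that. The plan nevertheless makes an efficacy power claim and lists it as a rigor safeguard.

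**Conclusion.** The point holds as an unsupported power statement that should be corrected. The tested effect, alpha and scale of d are all missing, and neither route found to reproduce 80-90% is power for a between-arm sleep-time difference of 0.48. If d=0.48 is such a difference, power at two-sided 0.05 with 25 per group and ρ=0.3 runs from 29% to 38% for the planned contrast and does not exceed 75% in the baseline-adjusted analyses examined. For d=0.51 the planned contrast has 32-42%, and the adjusted T2/T3 mean reaches about 80% at best. For fatigue (d=0.79), baseline-adjusted analyses give 82% or more, but the planned contrast stays at 64-78%.

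The omissions are certain. The specific percentages depend on the assumed alpha and on d being a between-arm difference. If d is within-group, power for the arm comparison cannot be computed from it.

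**What to change.** Keep N=60. Replace the power sentence with one that names the between-group test, alpha and scale of d, and gives the power for that test. For example:

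> With 25 per group, correlation 0.3 and two-sided alpha 0.05, the SMID vs usual care pre-to-post contrast has 80% power for a difference of 0.96 single-visit SD (95% CI half-width about 0.67 SD). Power for d=0.48 is 29% if d is a between-arm difference in single-visit SDs, or 38% if it is in change-score SDs.

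Once the source of d is confirmed, keep only the value that applies; if d is within-group, drop both and recompute from a between-arm assumption. If the sponsor prefers a baseline-adjusted analysis, the Data Analysis Plan must say so. The single-visit-scale figures are then 41% at one visit (detectable difference 0.77 SD) or 60% for the T2/T3 mean (0.61 SD). If 80-90% was computed for a time effect, or with f=d/2, say so and do not present it as power for the between-group hypothesis at d=0.48. A sentence that a non-significant result is not evidence of no effect would help but is optional.

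The cost is wording only, with no added participants or procedures. The downside is a less favourable stated power.
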